PNs will be trained to initiate as many encounters as needed to assist patients to complete CRC screening; however, a minimum of 2 telephone calls will be placed to all participants randomized to this group. The initial call will be placed approximately 2 weeks after mailing of the DVD to allow time for receipt and viewing of the DVD. During the initial call, the PN will use the web-based counseling protocol to first assess whether the participant has viewed the DVD. If the participant has not yet viewed the DVD, the PN will remind him or her to do so, answer any questions about accessing it, and reschedule the call for a later date. If the participant has viewed the DVD, the PN will then counsel to answer any questions and increase the participant’s knowledge of CRC screening, risk factors, and the benefits and harms of each screening test. **The PN will then focus on assessing and reducing barriers to CRC screening and enhancing access.** The web-based protocol will generate a checklist of topics and suggested talking points for PNs to use during each call. All encounters between the PN and the patient, as well as activities and contacts with others (GI resource nurse, primary care provider, community resources) that the PN initiates on behalf of the patient will be documented in the web-based documentation system. A sample of the PN tracking and documentation system as well as content covered in PN calls is included elsewhere.

For patients who request a FIT, the PN will mail the test and place a follow-up call to answer questions about the test and encourage completion. Although there may be more intervening phone encounters, the PN will call participants who schedule a colonoscopy 1-2 days prior to their appointment. During this call, PNs will focus on: 1) reviewing the colonoscopy procedure and what the participant will experience; and 2) providing support and guidance for completing the bowel preparation, including managing dietary and medication restrictions. Although the protocol will provide structure for the PN calls, PNs will have complete flexibility to respond to and document participants’ specific questions, needs, barriers, and concerns. In addition, PNs will record all actions taken to assist participants in the web-based documentation system.

**C.4.c. Training of Patient Navigators.** PNs will be IU School of Nursing research RNs who are familiar with the study protocol and knowledgeable about CRC. They will have prior patient engagement experience. Initial training will be a half-day session presentation by our Ohio State University co-investigators, [name] and [name], who are experts in navigation. Training objectives will be to have PNs: 1) understand the principles of patient navigation; 2) understand the scope of their role; 3) deliver barrier reducing messages to promote CRC screening uptake; 4) prepare participants scheduled for a colonoscopy; and 5) assist participants in completing a stool blood test (FIT). The Eskenazi Endoscopy Patient Navigator nurse will attend the training session and provide information on local resources that she currently uses for transportation, financial assistance, etc. This session will also include a presentation on intervention fidelity and quality assurance by an Ohio State co-investigator. A second half-day session will be conducted by the study's Clinical Research Coordinator. The DVD intervention will be viewed so that navigators are refreshed on what colon health information patients will receive prior to their contacting them. In this session, PNs will also practice delivering the phone scripts, making entries into the training version of the REDCap PN database, and role-play common patient scenarios likely to be encountered. PNs will practice and role-play until they have reached 100% compliance with the intervention protocol. After the initial training sessions, monthly conference calls will occur among the PNs, Clinical Research Coordinator, and the Ohio State PN quality assurance monitor. The calls will include additional training, a Grand Rounds case presentation, and the opportunity to discuss any concerns related to patient navigation. From these discussions, future training topics will be identified. Potential monthly training topics include: 1) addressing challenging situations; 2) revisiting patient empowerment approaches; 3) health literacy; 4) self-care: approaches to avoid feeling burned out; 5) time management; and 6) updates on community resources.

**C.5. Intervention Pretesting (RQ-2, PC-1, PC-3).** Usability testing will occur with individual user feedback from members of the target audience. We will recruit 5 patients from our target population for individual user testing. Usability of the tailored DVD will be evaluated by assessing ease of use, content (leveling and appropriateness), aesthetic appeal, and cultural relevance. We will present prototypes of both interventions to our CAB (who represent our target population) as components are designed. The information gathered during individual user testing will be used to revise both interventions.

**C.6. Intervention Delivery (RQ-2).** The tailored DVD program will be made available to subjects in two formats: DVD and a web version. At the start of subject accrual, the program will be limited to DVD format. During the baseline interview, participants will be asked about access to a DVD player. For patients who have access to a DVD player, we will mail the tailored DVD. Since the numbers of patients who have access to the Internet is growing, and DVD players may be less common in the future, we will also make the tailored interactive program available for viewing online via the Internet for people who have such access. A Gallup poll conducted in 2013 showed that 80% of U.S. homes have a DVD player and 73% have Internet access. For those who have access to both a DVD player and the Internet, the format for delivery of the tailored DVD will be based on participant preference. The DVD, or link to the website, will be mailed directly to participants' homes after the baseline interview is completed. A letter will be included that instructs participants to view the DVD within the next 2 weeks and provides a toll-free number to call for technical assistance if needed. Trained research assistants and the project manager will be available to provide technical assistance to any participant who has difficulty viewing the DVD or accessing the tailored program online. If neither of these technologies is available in the home, through family or friends, or at the public library, we will loan portable DVD players to participants along with enclosed instructions and mailers for returning players to the research office.

Patient navigators will begin contacting participants by phone about 2 weeks after mailing the DVD to set up an initial phone appointment, depending on the participant's preference and availability. PNs will be trained to make as many contacts as needed to assist patients to complete CRC screening; however, a minimum of two calls will be placed to all participants randomized to the tailored DVD plus PN group. If navigators are unable to reach participants by phone, a letter will be mailed requesting that participants contact them.

**C.7. Intervention Fidelity. (RQ-2)** Published recommendations to ensure intervention fidelity address five components that are described below. **1) Study design.** The three group design ensures blinding of outcome data collectors to

participant group assignment, as feasible. 2) PN training. Training is addressed in Section B.6 above. 3) Intervention delivery. To ensure consistency of intervention delivery, evaluation of intervention processes is essential and several strategies will be used. DVDs or instructions with a link to view the program on the web will be mailed to participants. All PN calls will be recorded for quality assurance purposes, with a subsample randomly selected for evaluation. Audiotaped PN calls will be evaluated using a checklist we developed in prior studies. Project staff will discuss intervention delivery issues, technical support requests, and any unusual events during biweekly research team meetings. Modifications will be made as necessary and recorded to ensure appropriate intervention delivery and maintenance of protocol integrity. Decisions about modifications will be made jointly by the research team and recorded. 4) Intervention receipt. Since all participants in the intervention arms will receive the tailored DVD via mail or a web link, we will call each participant approximately 2 weeks after mailing to conduct a process evaluation of this intervention. Through the process interview, we will assess receipt of the DVD or web link, how much of the DVD was viewed (none, part, or all), as well as satisfaction with and relevance of the content for those assigned to both intervention groups. Participants will receive a \$50 gift card for completing this process interview. Specific evaluation questions that assess user experience and satisfaction are included elsewhere. 5) Intervention enactment. All participants who return a completed FIT will have enacted the behaviors recommended in the interventions. Those who attend a colonoscopy appointment are routinely asked about their experience with, and ability to complete the bowel preparation and refrain from eating solid food before the test. This information is documented in the EMR, and colonoscopy procedure notes will provide evidence that participants who choose this test have enacted the behaviors recommended in the interventions. **The PN documentation record will provide additional data to support intervention enactment by participants assigned to this group.**

**C.8. Data Collection. (RQ-6, PC-2, PC-3)** Trained data collectors/interviewers who are employed by the Indiana University Center for Survey Research (CSR) will collect data via structured telephone interviews. Interviews will be conducted at baseline (T1), at 6 months post-baseline (T2), and at 9 months post-baseline (T3). If unable to reach participants when a phone interview is due, we will mail a letter to them requesting that they contact the CSR data collection team so that the interview may be completed. Reminder letters will be mailed to participants about 1 month before the T2 and T3 interviews are due. Process interviews will be conducted with participants assigned to the DVD intervention group approximately two weeks after mailing of the DVD. The baseline interview includes a question to confirm age eligibility and assesses the following: demographics, health literacy, health status, patient activation, CRC knowledge, CRC fear, cancer fatalism, colonoscopy-related procedural anxiety, social support, and media exposure. For both colonoscopy and FIT, the baseline interview asks questions about participants' experience with each test and readiness to screen by each test. Health beliefs for perceived CRC risk and colonoscopy and FIT perceived benefits, perceived barriers, and perceived self-efficacy are also collected. At completion of the baseline interview, participants will be randomized. People assigned to DVD or DVD + PN intervention groups will be told they will receive a DVD or instructions to access the website to view the program (based on their preference). Those in the tailored DVD + PN group will also be told they also will receive a phone call from the nurse navigator in about a week.

The DVD process interview will assess receipt of, viewing of, and satisfaction with the DVD and will be done approximately 2 weeks post-mailing of the DVD. Receipt, experience and satisfaction with the PN intervention, for those randomized to the DVD+PN group, will be assessed as part of the 6 month interview (T2). The 6 month interview will also assess changes in knowledge, patient activation, CRC fear, cancer fatalism, and colonoscopy-related procedural anxiety. Health beliefs for colonoscopy and FIT will be assessed as will self-reported CRC screening intention, uptake and satisfaction with the screening experience (for those who completed screening). At 9 months, we will assess self-reported CRC screening intention, uptake and satisfaction with the screening experience (for those who completed screening since T2). Participants will receive a \$50 gift card for the baseline interview, a \$50 gift card for the 6 month interview and a \$50 gift for completing the 9 month interview; a total of \$150 for participants who complete all three interviews. Participants who complete the additional DVD process interview will receive another \$50 gift card for a total of \$200 in gift cards. By using gift cards with an appealing dollar amount over the 9 month data collection period, we hope to incentivize participants to remain in the study. Additional retention strategies which we will use include mailing

participants a magnetic, refrigerator clip customized with the ACT Study name, phone number, and message “Working Together for Better Health”. The refrigerator clip will serve as a visible reminder of their participation in the study and provide a convenient way for them to know how to contact us. Participants will also be mailed newsletters and a birthday card. Our Research Assistants will make “check-in” calls to thank participants for continuing in the study, ensure that the gift card incentive was received, confirm that they have a working DVD player (if randomized to the DVD only or DVD + Patient Navigator group), remind participants of the next step, answer questions, etc. These brief calls are scheduled to occur at 4 different times over the 9 month time frame in order to keep participants continually engaged. For participants who miss who the DVD process interview, 6 month follow-up interview, or Patient Navigation intervention, we will mail them a letter. This letter lets participants know that we understand that it's not always possible to complete a study procedure when due and reassures them that they can still be in the study. By sending this letter, we hope to counteract any inclination participants may have about dropping out of the study because they missed a step.

Table 3 on the following page describes the measures and data collection timeline.

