**C.2. Design.** A three-group randomized controlled trial will be conducted to compare the effectiveness of two interventions to promote CRC screening test completion. Eligible men and women who were scheduled for colonoscopy in the endoscopy unit at Eskenazi Health (our safety net health system) but did not attend their appointment will be invited to participate. After baseline data are collected via structured telephone interviews, participants will be randomized to receive: 1) a mailed DVD titled *Time to ACT: Approaches to Colon Testing*; 2) the mailed DVD plus a patient navigator (PN) intervention; or 3) usual care (See Figure 2). (RQ-2, RQ-3, RQ-4, RQ-5)

Study Design and Schema

**C.3. Setting and Recruitment. (PC-2)** On a weekly basis, Eskenazi Health IT department will generate lists of age-eligible patients at average risk who did not attend their colonoscopy appointment. The list will include 2 groups of average risk patients who missed their appointment: 1) patients who had a colonoscopy screening ordered; and 2) patients who had a recent fecal immunochemical test (FIT) that was positive with a follow-up order for colonoscopy. Due to differences in physician ordering practices, the follow-up colonoscopy can be ordered as a colonoscopy screening, colonoscopy diagnostic, or colonoscopy high risk. Patients will be approved for contact by [name], Director of the Eskenazi Health Endoscopy Department. Patient information will be released to the study’s data manager, the Eskenazi Endoscopy Department’s Patient Navigator nurse, and trained research staff at the IU School of Nursing using secure electronic data transfer methods. Information disclosed is limited to that which is necessary to determine eligibility and to contact patients by mail and telephone. As a first step, the Endoscopy Patient Navigator nurse or nurse designee will screen patients by looking back 10 years and excluding any with a history of adenomatous polyps, sessile serrated polyps, or any mass suggestive of neoplasia. Patients with a history of hyperplastic polyps, lymphoid tissue, or no polyps will be

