recruited. To be eligible, these patients must: 1) have been referred for a colonoscopy that was not done (i.e, canceled or no show); and 2) be 50 to 75 years old if non-African American or 45-75 years old if African American. Patients meeting these inclusion criteria will be excluded for the following reasons: 1) unable to speak, read, and write English; 2) a personal history of having a colonoscopy at a non-Eskenazi Health location where polyps were found and they were the type that could turn into cancer; 3) FIT negative result in the past 12 months; 4) a personal history of CRC; 5) a personal history of conditions that place them at high risk for CRC such as ulcerative colitis, Crohn's disease, or known hereditary syndromes such as familial adenomatous polyposis or hereditary nonpolyposis colorectal cancer; 6) a family history of CRC which increases their risk; and 7) speech, hearing, cognitive, and/vision impairment. Trained research staff at the IU School of Nursing will recruit patients using procedures consistent with clinic and HIPAA requirements. Recruiters will send introductory letters, signed by the Principal Investigator and a co-investigator who is a member of the Eskenazi Medical Staff, along with a recruitment brochure and Study Information Sheet that explains the study to all approved patients. The letter informs patients that they will receive a phone call about the study within the next week unless they call a toll-free number to say they do not wish to be contacted. One week after letters are mailed, trained recruiters at the IU School of Nursing will call potentially eligible participants who have not opted-out to explain the study requirements, potential risks and compensation, and answer questions. Adequate speech, hearing, and cognition of potential participants will be confirmed by recruiters based upon the phone conversation. They will then proceed to determine eligibility, obtain both verbal informed consent and verbal HIPAA Authorization, and schedule a convenient time to conduct the baseline interview. Each participant who is not reached will be called back up to, but no more than, 10 times. Recruiters will record each call attempt including the date, time, disposition, and callback preference. Participants who decline to participate will be thanked for their time, with their response and reason for refusal recorded.

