**PRIMARY OUTCOME MEASURES: (RQ-6, PC-2, IR-4)**

**Completion of any CRC screening test** (fecal immunochemical test (FIT) or colonoscopy) will be measured by medical record review. FIT and colonoscopy completion dates will be extracted from the electronic medical record. Because self-report of CRC screening has correlated well with medical record data, we will also use validated items from our previous research to ask participants if they have had a CRC screening test (FIT or colonoscopy) as well as their plan to have one in the next 6 months (only for those who have not yet completed screening).

**Quality of bowel preparation** will be assessed two ways for those participants who attend their colonoscopy: 1) by participant self-report of their bowel prep experience and 2) via review of electronic medical records. When patients arrive in the endoscopy department, a nurse assesses their experience with the bowel preparation and adherence to dietary restrictions. Patients who report they were unable to complete the bowel prep or have eaten in the past 24 hours are considered inadequately prepped for the procedure and sent home. These patients must repeat the preparation to cleanse the bowel and reschedule their colonoscopy. For those who report successful completion of the bowel prep and adherence to dietary restrictions, quality of the bowel preparation (i.e. degree of cleanliness/emptiness of the bowel) is evaluated by the endoscopist during the colonoscopy. Standard practice is to evaluate bowel preparation quality using an assessment similar to the Aronchick 5-point scale where 1=*excellent*, 2=*good*, 3=*fair*, 4=*poor*, and 5=*inadequate*. Adequate is a term that may also be used to describe the quality of bowel preparation as a single descriptor or in addition to the Aronchick assessment as excellent (1), good (2), or fair (3). Procedural notes including endoscopists' ratings of the quality of the bowel prep are entered into ProVation, a menu-driven software program. Therefore, participants will be considered inadequately prepped if they are: 1) deemed inadequately prepped from self-report during initial nursing assessment OR 2) if the endoscopist rates the quality of the bowel prep as poor (4)

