**C.13. Data Analyses. (IR-3, IR-5, MD-3, MD-5, HT-1, HT-2, HT-3, HT-4)** Preliminary analyses will compare baseline demographic information across groups using means and standard deviations for continuous variables and frequency distributions for categorical variables. We will adjust for those characteristics in subsequent analyses if significant differences emerge at a conservative level for inclusion of a covariate ( $p < .20$ ). Characteristics of participants who drop out by 9 months will be compared with those who remain to determine what biases may exist. **(MD-4)** The above analyses will be conducted using ANOVA, chi-square tests, or exact or non-parametric equivalents. If there appear to be biases in dropout, we will conduct pattern mixture models analyses to see how the results could change based on the MAR assumption **(IR-5, MD-2, MD-3, MD-5)**. Primary analysis of outcomes will employ an intent-to-treat analysis; all participants will be included regardless of compliance with interventions. The main outcome, CRC screening completion with any test (FIT or colonoscopy) will be extracted from medical records for all participants, including those who drop out or are lost to follow-up. Intervention exposure will be measured and its effects will be accounted for in the intent-to-treat analysis. First, we will know whether participants viewed none, part, or all of the DVD. Second, we will document how many contacts PNs make to or on behalf of participants assigned to that group. These variables (viewed none/part/ or all of the DVD and number of navigator contacts) will be added as covariates in analyses. For all aims, sensitivity analysis will be conducted as needed for each outcome to assess the effects of the model assumptions on the results **(IR-5)**. Assumptions, such as normality of residuals, will be checked and appropriate modifications to the analysis plan applied if needed, such as transformations or use of non-parametric methods. From our prior studies, we expect missing data to be minimal (less than 2%) for subjects during participation. For missing data on scales, we will use mean imputation as long as two-thirds of the questions have been answered (or per validated instrument instructions, if otherwise). **(MD-2, MD-3)**

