For Aim 1, we will test the primary hypothesis related to comparing intervention effects among the three randomized groups (H1.1: PN+DVD vs. DVD only and H1.2: PN+DVD vs. usual care and DVD only vs. usual care) using the outcome of completion of CRC screening using any test at 12 months post-baseline. In addition, quality of bowel preparation, procedural anxiety, and satisfaction with the screening experience will be examined as outcomes. As an initial assessment of CRC screening completion at 12 months, we will use a chi-square test for a 3 x 2 (group by screening completion) contingency table to test whether completion rates differ across groups. If the  $p$ -value for the overall test is significant at the .05 level, pair-wise 2 x 2 tests will be conducted at the  $.05/3 = .017$  level. However, the primary analyses for Aim 1 will involve fitting multivariable logistic regression models of the primary outcome of 12-month CRC screening test completion (yes/no). Independent variables will be group assignment and continuous and categorical individual characteristics. These models will also allow us to investigate intervention effects on CRC screening test completion while adjusting for potential confounders. Group assignment will be coded using dummy variables with usual care as the reference category. For H1.3, quality of bowel preparation will be analyzed for those participants who complete colonoscopy with proportional-odds ordinal logistic regression using an ordinal dependent variable ( $1 = \text{excellent}$ ,  $2 = \text{good}$ ,  $3 = \text{fair}$ ,  $4 = \text{poor}$ ,  $5 = \text{inadequate}$ ). If some outcome categories are sparse, the outcome will be dichotomized into adequate

(*excellent or good*) versus inadequate (*fair, poor, or inadequate*). The outcomes of anxiety and satisfaction are continuous outcomes and will be modeled with linear regression.

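### A repeat FIT counts as screening completion for patients enrolled because a positive FIT was not followed by the ordered colonoscopy, and no planned analysis separates them

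*Combined protocol and SAP*

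**What the plan says.** **Entry.** C.3, E.3 and the recruitment text under Protection of Human Subjects describe two source groups. The second is "patients who had a recent fecal immunochemical test (FIT) that was positive with a follow-up order for colonoscopy". The order type does not identify this group, because "the follow-up colonoscopy can be ordered as a colonoscopy screening, colonoscopy diagnostic, or colonoscopy high risk". The exclusions in C.3 do use FIT results: a "FIT negative result in the past 12 months" excludes a patient, and a positive one does not.

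**Endpoint.** C.9 defines completion of any CRC screening test ("fecal immunochemical test (FIT) or colonoscopy) will be measured by medical record review"). C.13 tests Aim 1 "using the outcome of completion of CRC screening using any test at 12 months post-baseline", with the outcome taken from the record for all participants. Neither section sets a condition on the baseline FIT result.

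**Intervention.** C.4.b states: "For patients who request a FIT, the PN will mail the test and place a follow-up call". C.4.c lists helping participants complete a FIT among the navigator training objectives. Neither statement is limited by baseline FIT result.

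**Analysis.** Randomization is stratified by sex, race/ethnicity and age (E.1). The moderators are age, race/ethnicity, sex and income (C.13, Aim 2). C.13 also says that "sensitivity analysis will be conducted as needed for each outcome to assess the effects of the model assumptions on the results".

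**The concern.** The entry rule and the endpoint rule treat the same event differently. A patient in the second group had already completed a FIT. It was positive, and the patient counted as still needing a test because the colonoscopy ordered afterwards was not done. Within the trial, a second FIT makes that patient a completer even if the colonoscopy is still undone. For this group, a success on the primary endpoint can leave the reason for enrolment unresolved.

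Two things are at stake. The first is what the completion rate means, and with it the safety of participants who have an unresolved positive test. The second is the comparison between arms. The DVD presents FIT in both intervention arms, but only PN+DVD is described as mailing kits and calling to encourage their return. Any excess of repeat-FIT-only completions in that arm would add to the PN+DVD advantage in H1.1 and in the PN+DVD part of H1.2.

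**Working it through.** **Tracing one participant through the text.** Positive FIT, colonoscopy ordered and missed: eligible under C.3. Randomized to PN+DVD, asks for a FIT: the navigator mails one (C.4.b). Returns it, has no colonoscopy within 12 months: completer (C.9, C.13). No stratification factor or moderator identifies this participant. The covariates in the Aim 1 regression are individual characteristics that are not listed. The sensitivity clause in C.13 concerns model assumptions, not which test counts.

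**Reproducing the plan's power.** Inputs from C.12: completion rates of 44% (PN+DVD), 20% (DVD) and 5% (usual care), n = 115 per group, two-sided alpha = 0.05/3 (z = 2.394). Continuity-corrected two-proportion test, with d the difference and p̄ the mean of the two rates:

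power = Φ{ [d − 1/n − z·√(2p̄(1−p̄)/n)] / √([p1(1−p1) + p2(1−p2)]/n) }

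For 44% vs 20%: (0.24 − 0.0087 − 2.394 × 0.0615) / 0.0594 = 1.41, so power is 92.1% (Table 4: 92%). The same formula gives above 99.9% for 44% vs 5% (Table 4: 99%) and 80.8% for 20% vs 5% (Table 4: 80%). Table 4 is reproduced.

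**Illustration.** Two inputs are not in the documents and are assumed:

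- f, the share of participants who entered after a positive FIT, from 0 to 20%.
- The excess of repeat-FIT-only completion in that group, PN+DVD over DVD, set at 24 points. This equals the planned overall difference (44 − 20) and is a convenience, not a limit.

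If those completions no longer count, the difference falls by 24f points. For simplicity, the whole fall is taken from the PN+DVD rate and DVD stays at 20%.

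| f | Points removed (24 × f) | PN+DVD rate | Participants per 150 | Power vs DVD |
|---|---|---|---|---|
| 0% | 0 | 44.0% | 0 | 92% |
| 6% | 1.4 | 42.6% | 2.2 | 88% |
| 10% | 2.4 | 41.6% | 3.6 | 85% |
| 20% | 4.8 | 39.2% | 7.2 | 75% |

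For f = 10%: (0.216 − 0.0087 − 2.394 × 0.0609) / 0.0592 = 1.04, giving 85%. For f = 20%: (0.192 − 0.0087 − 2.394 × 0.0602) / 0.0589 = 0.67, giving 75%.

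These figures describe an analysis that does not count repeat-FIT-only completions in this group. They do not describe the primary analysis as defined, which counts them.

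**The case against.** **The endpoint is behavioural by design.** The trial's premise is that people who miss colonoscopy should be offered alternatives, and C.3 calls both entry groups average risk. On that view a returned FIT is the intended result. This stands to the extent that extra FIT returns under PN+DVD are a real effect on the endpoint as defined. A reader might infer that the primary result is biased or mismeasured. The documents do not support that: the outcome is read from the record in the same way in every arm, and randomization balances the entry groups on average. No passage says outright that a repeat FIT is inadequate after a positive one. What the plan does show is that a colonoscopy was ordered as follow-up and was still outstanding at entry.

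**A colonoscopy-only comparison is already named.** H1.1 and H1.2 include colonoscopy alone, where a repeat FIT cannot count. This helps only in part. The comparison pools both entry groups and drops FIT completions in participants with no positive FIT, for whom FIT is a proper endpoint.

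**The group may be very small.** A reader might infer this from section B, where all 48 patients interviewed before the trial said that their provider had offered no test besides colonoscopy. Those interviews record what patients said they were offered in a separate preliminary study. They do not count positive FITs, and the trial names positive-FIT patients as a recruitment source. They set no upper limit on the share. It may be zero, but neither that nor a negligible effect on power can be claimed from the documents.

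**Navigators may already be told what to do.** They are research nurses with access to the endoscopy nurse for medical questions and test results (Consortium Contractual Arrangements), and C.4.b says that the call content is included elsewhere. A rule against mailing a repeat FIT may exist there. This stands, so the navigator request is to confirm first.

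**The fidelity text is weak support.** C.7 says "All participants who return a completed FIT will have enacted the behaviors recommended in the interventions". That defines enactment, not the endpoint, and the point does not depend on it.

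**Conclusion.** The point holds as a matter of endpoint meaning and patient safety. As written, a participant with a positive FIT and an outstanding follow-up colonoscopy becomes a success by repeating the FIT, and nothing planned would show how often this happened or in which arm. That conclusion comes from the text and needs no assumption.

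Its size cannot be determined from the documents. The tabulated range of 92% down to 75% rests on assumed shares of 0 to 20% and an assumed 24-point excess. A larger share or excess would lower power further, and a share or excess of zero would leave it unchanged. Confidence is medium. The change should be made, but the primary endpoint need not be altered.

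**What to change.** 1. **Flag.** Identify participants whose qualifying colonoscopy order followed a positive FIT. Use the baseline FIT result in the EMR, not the order type, and the same look-back that recruitment uses for a recent FIT. C.3 states no window, so the one used should be written down.
2. **Report** the flag by arm.
3. **Sensitivity analysis.** Add to C.13, before outcomes are examined by arm, a repeat of the primary analysis in which only a completed colonoscopy counts as completion for flagged participants. They stay in the denominator. Leave the primary endpoint unchanged.
4. **Navigator protocol.** Confirm that it directs flagged participants to colonoscopy and does not mail them a repeat FIT. If that instruction is absent, add it and record the date, because it slightly changes the intervention for later enrollees.

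The cost is one EMR variable, one extra analysis and, at most, one added instruction. FIT and colonoscopy completion dates are already extracted, and FIT results already bear on eligibility. The sensitivity analysis may count slightly fewer events and so have somewhat less power than the primary analysis.
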